Note: * = modified to be consistent with DSM-5 criteria. The post-group assessment corresponds to completion of the treatment/placebo groups.

2a.3.j. Planned Data Analysis.

Generalized Linear Mixed Modeling (GLMM) will be used as the primary data analytic approach for Aims 1 and 2. We believe this approach will provide the most parsimonious test of our hypotheses based on the following considerations. First, we considered only evaluating outcomes at the 6-month follow-up. While this approach would provide information regarding long-term outcomes, it has significant limitations including: (a) increased potential for attrition and missing data, and (b) loss of knowledge regarding outcomes immediately after the quit attempt (i.e., 2-weeks, 4-weeks). For these reasons an analysis focusing solely on the 6-month follow-up would not provide the most reliable and powerful test of the hypotheses. Second, *GLMM allows for modeling slope and change over time. This approach will allow us to model change in substance use and sleep over the course of short-term (2-weeks, 4-weeks) and long-term (6-months) follow-up, while also allowing us to model any unpredicted change in substance use (e.g., cannabis) during the treatment/placebo phase.* Based on these considerations we opted to conduct the primary analysis for Aims 1 and 2 by evaluating change over time through the use of GLMM. This analytic approach is favorable for a number of reasons including its ability to include all available data, not just data from patients who complete assessments. In addition, we will conduct secondary analyses for each hypothesis to evaluate group differences at each time point.

To account for family wise error, alpha will be adjusted in all secondary analyses. *Importantly, over the course of group CBT-I (or placebo group), we will track participants' substance use, including cannabis, and sleep. We will model all outcome data from the start of the intervention. This approach will allow for modeling any unpredicted changes in cannabis use (i.e., increase or decrease in use) during the intervention portion of the study.* Below we provide a detailed overview of how GLMM will be employed for Aims 1 and 2.

Aim 1:

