Hypothesis 1.1. Veterans who receive either *CBT-I-MA* or *CBT-I* prior to a cannabis cessation attempt will evidence a greater reduction in cannabis use frequency over the three post-quit attempt assessments (2-weeks, 4-weeks, and 6-months post-quit day) as compared to those who receive *PC*. In order to test this hypothesis a mixed-effects regression will be used to model changes in the dependent variable (frequency of cannabis use) across time as a function of group membership and baseline values (fixed effects) with a random effect for person to account for repeated measurements; frequency of cannabis use (obtained from TLFB; See 'measures' section for details).

As a secondary analysis, we will conduct an *analysis of covariance (ANCOVA; alpha set to .01)* to examine group differences in cannabis use frequency at each time point (2-weeks, 4-weeks, and 6-months post-cessation).

Hypothesis 1.2. Veterans receiving either *CBT-I-MA* or *CBT-I* will have greater point prevalence abstinence (PPA) over the three post-quit attempt assessments (2-weeks, 4-weeks, and 6-months post-quit day) compared to those receiving *PC*. In order to test this aim we will evaluate the differences in PPA between *CBT-I-MA* and both *CBT-I* and *PC* groups, and *CBT-I* and *PC* groups across the three follow-up assessments (2-weeks, 4-weeks, and 6-months post-cessation). This will be conducted through the use of a mixed-effects logistic regression.

As a secondary analysis, we will conduct three chi-square analyses to examine group differences in rates of PPA at each of the three time points (2-weeks, 4-weeks, 6-months post-cessation).

Exploratory Hypothesis. *In terms of the above cannabis outcomes, those who receive CBT-I-MA will evidence better outcomes (reduced frequency and greater PPA) as compared to those who receive CBT-I. Results related to this hypothesis will be determined through analyses conducted for the primary hypotheses (Hypothesis 1.1 and 1.2).*

Secondarily, we will conduct exploratory analyses to examine factors (e.g., adherence, dose) that account for differences observed between the *CBT-I-MA* and *CBT-I* groups in relation to cannabis outcomes through the use of mediation models. Mediators of interest will include adherence (measured by session attendance), and dose.

Aim 2:

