Hypothesis 2.1. Veterans who receive either *CBT-I-MA* or *CBT-I* prior to a cannabis cessation attempt will evidence improved sleep quality, as indicated by self-report and objective measures, over the three post-quit attempt assessments (2-weeks, 4-weeks, and 6-months post-quit day) as compared to those who receive *PC*. In order to test this hypothesis, two mixed-effects regressions will be conducted, one for self-report sleep (see 'measures' section for details) and another for objective indices of sleep (see 'measures' section for details). First, we will model changes in the dependent variable (self-report or objective sleep) across time as a function of group membership and baseline values (fixed effects) with a random effect for person to account for repeated measurements (random effects).

As a secondary analysis, four ANCOVAs will be conducted to examine differences in self-reported sleep quality between groups at each time point (following 6-week treatment/placebo group, 2-weeks, 4-weeks, 6-months post-cessation attempt). A series of four additional ANCOVAs will then be conducted to examine group-based differences in objective sleep at each time point (following 6-week treatment/placebo group, 2-weeks, 4-weeks, 6-months post-cessation attempt). All ANCOVAs will adjust alpha to account for family wise error rate.

Hypothesis 2.2. *Group based differences in cannabis outcomes averaged across the three post-quit attempt assessments (2-weeks, 4-weeks, and 6-months post-quit day) will be explained*

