by average sleep quality (self-report and objective) averaged across the three post-quit attempt assessments. To address the second hypothesis of aim 1, GLMM will be used to evaluate the mediating role of (a) self-report sleep quality averaged over time (b) objective sleep quality over time (2-week, 4-week, and 6-month post-cessation follow-ups). The MacArthur model of mediation will be used as this model, compared to Baron and Kenny's approach, is not based on a linear model. In addition the longitudinal design allows for determination of the temporal precedent of our mediator to the predictor variable, thereby meeting criteria for the MacArthur approach (Kraemer et al., 2008). Specifically, two independent models will be conducted. First, we will evaluate self-report sleep quality over time on the relation between group and average cannabis use frequency over time. Three steps will be conducted using mixed models. First, we will examine the relation between group and cannabis use frequency over time (path C). Second, we will examine the relation between group and self-reported sleep quality over time (path A). Finally, we will enter both group and self-reported sleep quality over time within the same model to predict frequency of cannabis use over time. Confidence intervals will be used to assess for significant partial mediation. Within the mediation model, the same series of steps will be conducted to evaluate the mediating role of objective sleep over time on the relation between group and cannabis use frequency over time.

Exploratory Hypothesis. *In terms of the above sleep outcomes, those who receive CBT-I-MA will evidence better outcomes (improved sleep quality) as compared to those who receive CBT-I. Results related to this hypothesis will be determined through analyses conducted for the primary hypothesis of Aim 2 (Hypothesis 2.1).*

Secondarily, we will conduct exploratory analyses to examine factors (e.g., adherence, dose) that account for differences observed between the CBT-I-MA and CBT-I groups in terms of sleep outcomes through the use of mediation models. Mediators of interest will include adherence (measured by session attendance), and dose.

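### All three arms are delivered as group therapy but no planned analysis has a therapy-group term, so arm contrasts on outcome level have standard errors that are too small if outcomes cluster by therapy group

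*SAP*

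**What the plan says.** SAP 2a.3 (Design Framework) schedules baseline assessments once enough people are available to fill three groups, and then runs six weekly sessions. The treatment descriptions in SAP 2a.3.b make all three conditions group-based. Protocol 8(m) puts each session at one hour.

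In SAP 2a.3.j, Hypothesis 1.1 models cannabis use frequency on arm and baseline value, "with a random effect for person to account for repeated measurements; frequency of cannabis use". Hypothesis 2.1 uses the same structure for sleep, "with a random effect for person to account for repeated measurements (random effects". Group membership in these models means the randomised arm. For abstinence in Hypothesis 1.2 the SAP says only "This will be conducted through the use of a mixed-effects logistic regression", and for mediation in Hypothesis 2.2 only "Three steps will be conducted using mixed models"; neither lists its random effects.

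The secondary tests are per visit: for use frequency, "analysis of covariance (ANCOVA; alpha set to .01"; for abstinence, "we will conduct three chi-square analyses to examine group differences in rates of PPA at each of the three time points"; and further ANCOVAs for sleep. On multiplicity the SAP says "To account for family wise error, alpha will be adjusted in all secondary analyses". On the time span it says "We will model all outcome data from the start of the intervention".

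The Power Analysis counts 56 independent people per arm. Neither it nor the Missing Data section gives a therapy-group size, an ICC or a design effect. The planned sensitivity analyses concern missing data and minimum dose.

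**The concern.** People in one therapy group share sessions, discussion and presumably a leader. If that makes their outcomes more alike than those of people in other groups of the same arm, the between-group variance enters the difference between arms, because each therapy group sits wholly within one arm. A person random effect handles repeated visits by the same person. It cannot carry between-group variance into the standard error of an arm contrast, and an ordinary ANCOVA or chi-square test cannot either.

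The contrasts exposed are those on outcome level:
- the per-visit secondary tests;
- the averages in Hypothesis 2.2;
- Hypothesis 1.2, if read as average abstinence;
- Hypotheses 1.1 and 2.1, if the visit-averaged arm effect is what is tested.

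For these, confidence intervals would be too narrow and false-positive rates above nominal.

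**Working it through.** **Inputs from the documents.** 168 randomised, 56 per arm; abstinence 20% versus 50%; d = 1.4 (Aim 1) and d = .56 (Aim 2); alpha .05; stated power .80 (all SAP Power Analysis).

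**Assumptions, not in the documents.** m = 6 to 8 people per group, hence 7 to 9 groups per arm (56/8 = 7; 56/6 ≈ 9); no loss; ICC of the analysed outcome .01, .05 or .10; two-sided tests. One group per arm per wave is inferred from the recruitment wording.

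**The plan's own figure.** For 20% versus 50% with 56 per arm, the pooled-variance normal formula gives (.30 − 1.96 × √(2 × .35 × .65/56)) / √((.16 + .25)/56) = (.300 − .177)/.0856 = 1.44, so power is .925. The stated .80 is an understatement. That is a separate matter, and .925 is the baseline used here.

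**Type I error of a pairwise level test.** Design effect DE = 1 + (m − 1) × ICC. The true standard error is √DE times the one used, so the actual error is 2 × (1 − Φ(1.96/√DE)).

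| ICC | DE, m = 6 | DE, m = 8 | Actual error at nominal 5% |
|---|---|---|---|
| .01 | 1.05 | 1.07 | 5.6-5.8% |
| .05 | 1.25 | 1.35 | 8.0-9.2% |
| .10 | 1.50 | 1.70 | 11.0-13.3% |

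Simulation under no arm effect agrees: about 5.5-6%, 8-9% and 11-14%.

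**The planned secondary tests.** Simulated with 0% or 20% loss, at ICC .01 / .05 / .10:
- Three-arm F test at the planned 1%: 1.1-1.4% / 2.1-3.3% / 3.8-6.5%.
- Three-arm chi-square at 20% abstinence, with an assumed adjusted alpha of .05/3 = 1.67%: 1.8-2.2% / 3.0-4.5% / 5.1-9.0%.

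Baseline adjustment does not remove this inflation.

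**Tests of change.** A constant group effect cancels. With a person-only random intercept, simulated error for the slope over the three follow-ups is 4.9-5.2%. If a group effect builds over the six sessions and the outcome is modelled weekly, a linear arm-by-week test gives 5.1-5.5% / 6.9-7.5% / 8.8-10.2%. By SAP Table 1 this can apply to timeline follow-back cannabis use and the sleep diary. It cannot apply to actigraphy or relapse status, which are not recorded weekly.

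**Power at ICC .05, 56 per arm.** Effective n = 56/DE, which is 44.8 at m = 6 and 56/1.35 = 41.5 at m = 8.
- 20% versus 50% abstinence: .925 falls to .858 (m = 6) and .830 (m = 8).
- d = .56, m = 8: .84 falls to .71 unadjusted. With an assumed baseline-outcome correlation of .5, the standardised effect is .56/√(1 − .25) = .647, and power falls from .92 to .83.
- d = 1.4, m = 8: power stays above .999.

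**Shared wave effects.** An effect common to all three groups of a wave cancels from the arm contrast. Comparing group means without a wave term nevertheless charges it to the error. With a wave-only ICC of .05 or .10, such a test at nominal 5% rejects about 2.3-2.9% or 1.3-1.6%. Pairing by wave gives 4.7-5.2%.

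**The case against.** The best defence is that the SAP frames its primary analysis as change over time, and a constant group effect leaves such a test at its nominal level. This stands for any test of change across the follow-ups. It does not cover the per-visit tests or the Hypothesis 2.2 averages. Nor does it settle Hypotheses 1.1 and 2.1: both carry baseline as a fixed effect, are worded as differences over the three follow-ups, and name no arm-by-time term. A reader might infer that the primary Hypothesis 1.1 test is certainly inflated. The documents do not support that, because they do not say which contrast is tested.

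Second, the ICC may be small. Exposure is six one-hour sessions, outcomes run to six months, and SAP 2a.3.b describes five hours a week of clinic group therapy that is not specific to an arm. This also stands: at ICC .01 the effect is minor. But the SAP neither states nor argues for a small value.

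Third, a reader might infer that the trial is underpowered. At 56 per arm and ICC .05 that does not follow. Abstinence power stays above .80, the Aim 1 effect is untouched, and the Aim 2 effect keeps .83 with the assumed baseline correlation; the .71 figure ignores the planned baseline adjustment.

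Last, the SAP is abstracted from a funding application, so silence on random effects in Hypotheses 1.2 and 2.2 may be brevity. It should be read as silence, not as a person-only choice. Hypotheses 1.1 and 2.1 do state their structure.

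**Conclusion.** Wrong as written, conditional on a therapy-group ICC above zero. The omission is plain in the text; its size is not known. Under the assumed group sizes with no loss, a nominal 5% pairwise level test runs at about 5.5-6% (ICC .01), 8-9% (.05) or 11-14% (.10). Only variance between therapy groups beyond a shared wave effect counts. The claim is confined to level contrasts, with one addition: change tests on weekly-measured outcomes, if a group effect builds during the sessions. It should be fixed because the correction is cheap and because a group-delivered trial analysed as independent individuals is open to challenge if positive.

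**What to change.** - In the mixed models for Hypotheses 1.1, 1.2, 2.1 and 2.2, add a recruitment-wave effect (fixed or random) together with a random intercept for therapy group (wave by arm). The wave term is needed so that shared wave variance is not charged to the arm contrast. Such variance is plausible, given about four years of recruitment and the protocol modification that dropped the motivation criterion.
- Add a therapy-group random slope only where arm-by-time is the tested term and the outcome is modelled from the start of the intervention.
- Use Satterthwaite or Kenward-Roger degrees of freedom for the linear models and a small-sample cluster correction for the logistic model.
- Take the per-visit secondary tests as contrasts from these models at the planned adjusted alpha.
- Restate power over a stated range of group size and ICC, with the planned baseline adjustment.
- Keep wave and therapy-group identifiers in the dataset.

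The cost is SAP wording and two data fields; sample size and procedures do not change. Intervals become slightly wider and the group variance will be imprecise. Degrees of freedom drop: with three arms and one group per arm in each of 7 to 9 waves, the wave-by-arm stratum has (3 − 1) × (7 − 1) = 12 to (3 − 1) × (9 − 1) = 16.

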In the event that groups differ in terms of potential confounding factors (e.g., psychological conditions, pharmacotherapy) exploratory analyses will be conducted to investigate these factors as moderators of the outcomes. Should moderation be demonstrated (i.e., significant effect size), we will use this information to formally power the next study to specifically test for these factors (Kraemer et al., 2002).

Power Analysis.

For this study, our primary aims are to investigate the impact of CBT-I-MA and CBT-I (compared to PC) on (a) frequency of cannabis use and PPA, and (b) self-reported and objective indices of sleep. We expect that group based differences in cannabis outcomes will be partially attributable to sleep. *In addition, we expect that CBT-I-MA will evidence better outcomes compared to CBT-I. Exploratory analyses will examine factors that may account for these differences.*

Existing empirical work has established medium to large effect sizes for the effect of therapist administered CBT-I on sleep outcomes among individuals with psychiatric comorbidities (Cohen's d's range from 0.56 – 2.20; Smith et al., 2005). *While no research has examined the effect size of CBT-I with an adjunctive mobile app, previous research has demonstrated a small/medium sized effect (Cohen's d's = 0.42) to observe differences in outcomes between treatment as usual for substance use disorders and treatment as usual with a technology-based adjunctive component (McKay et al., 2010).* In addition, no research has examined the impact of CBT-I on cannabis use outcomes. However, previous work has demonstrated that sleep disturbances resulting from withdrawal from cannabis use are attenuated through sleep interventions (Cohen's d's range from 1.4-2.4; Vandrey et al., 2011).

Based on these established effects, we conducted a power analysis to determine the necessary sample size to detect the hypothesized effects. To begin, power calculations were based on the hypothesis related to tests of mediation on the relation between group and sleep outcomes, as this would require the greatest sample size to detect the established effect size given the required analyses. Based on established methods to calculate power for mediation, *a sample of 168 Veterans would be required to detect a small/medium mediation effect with a power of .80 and alpha of .05*. This sample size would allow for the ability to detect the additional expected effects for Aims 1 and 2.

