In terms of the primary hypothesis of Aim 1 (Hypothesis 1.1), *the impact of CBT-I-MA and CBT-I on frequency of cannabis use post-cessation, we based our power calculations on an ANCOVA with the inclusion of 3 covariates as this would provide an overestimation of the sample size required for the GLMM analysis. A sample of 168 individuals would allow for a detection of a significantly smaller effect in terms of the primary aim ($d = .42$), providing confidence in our ability to detect the hypothesized effect of $d = 1.4$. This sample size will also allow for adequate power to detect group differences between CBT-I-MA and CBT-I ($d = .42$; Aim 1 Exploratory Hypothesis)*.

In terms of the secondary hypothesis of Aim 1 (Hypothesis 1.2), *the impact of CBT-I-MA and CBT-I on PPA, we used power calculation software to calculate the effect size based on a test of independent proportions. With an estimated abstinence rate of 20% within the placebo condition (PC; based on previous research; Marijuana treatment project research group, 2004), and alpha of .05, 168 Veterans (56 per group) will allow for power of .80 to detect a 30% difference in the prevalence of abstinence in the CBT-I group. As we conservatively estimate a 50% abstinence rate in the CBT-I condition, we will have enough power to detect the expected effect*.

In terms of Aim 2, investigating the role of CBT-I-MA and CBT-I on subjective and objective sleep quality, *we based our power analysis on an ANCOVA with the inclusion of 3 covariates and 3 groups as this would overestimate the required sample size needed within GLMM models. A sample of 168 individuals would allow for a detection of a smaller effect in terms of the primary aim ($d = .42$), providing confidence in our ability to detect the hypothesized conservative effect of $d = .56$. This will also allow for adequate power to detect group differences between CBT-I-MA and CBT-I ($d = .42$; Aim 2 Exploratory Hypothesis)*.

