Therefore a total sample of 168 will be adequate to detect all expected effects. An intent-to-treat approach will also be used. Therefore, all individuals randomized will be included in analyses. In the event that a set of individuals do not receive a minimum intervention dose (i.e., attend 70% of group sessions; Litt et al., 2007; Project Match Research Group, 1997), we will conduct analyses with and without these individuals. This sample size is feasible over the course of 4 years as evidenced in previous work conducted among outpatient substance use research protocols (Heinz et al., 2013).

Missing Data. Based on our protocol to limit participant attrition, we expect relatively little missing data over the 6 months of this study. We will limit the effect of missing data both methodologically and statistically. *First, we will account for 10% loss prior to randomization. Therefore, we will aim to recruit 187 individuals, with the goal of randomizing 168 individuals for the intent-to-treat analyses. Second, we chose to model our data using a GLMM approach as this method allows for multiple missing data points within longitudinal designs making this a robust analytic method for handling missing data. Additionally, as it is likely that not all participants will be included in analyses due to missing data, we will examine the reliability of the results by re-conducting analyses on complete data sets obtained through multiple imputation procedures and pooling*

results (Graham, 2012). Sensitivity analysis will then be conducted to examine the impact of missing data on outcomes (Carpenter et al., 2007).

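### The SAP says 168 Veterans give adequate power at d = .42, including for the app comparison; its own ANCOVA basis gives about 60% to 72% without covariate gain

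*SAP*

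**What the plan says.** The SAP's Power Analysis (within 2a.3.j, Planned Data Analysis) makes the d = .42 claim for three purposes.

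- **Hypothesis 1.1, cannabis use frequency.** The basis is an ANCOVA with 3 covariates, described as overstating the sample needed for the mixed model: "A sample of 168 individuals would allow for a detection of a significantly smaller effect in terms of the primary aim ($d = .42").
- **Aim 2, sleep.** Here "we based our power analysis on an ANCOVA with the inclusion of 3 covariates and 3 groups", again described as conservative, with the result: "A sample of 168 individuals would allow for a detection of a smaller effect in terms of the primary aim ($d = .42").
- **CBT-I-MA against CBT-I, exploratory under both aims.** For Aim 1: "This sample size will also allow for adequate power to detect group differences between CBT-I-MA and CBT-I ($d = .42"), and the same for Aim 2.

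The section concludes: "Therefore a total sample of 168 will be adequate to detect all expected effects".

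No power value is attached to d = .42. Where the SAP does name a power level it is .80 with alpha .05. It does so for mediation ("a sample of 168 Veterans would be required to detect a small/medium mediation effect with a power of .80 and alpha of .05") and for abstinence, where it also gives the allocation of 56 per group. It states neither sidedness nor a covariate R².

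The planned primary model for Hypothesis 1.1 describes change "across time as a function of group membership and baseline values (fixed effects) with a random effect for person to account for repeated measurements". No baseline-to-follow-up or between-visit correlation is given.

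**The concern.** A calculation offered as conservative should itself deliver the sensitivity claimed. Fifty-six against 56 looks too few for 80% power at d = .42, and the other contrasts look short too.

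For the primary contrasts, d = .42 is only a margin below the hypothesised effects (1.4 for cannabis frequency, .56 for sleep). For the app comparison it is the expected effect itself, taken from earlier work on technology-based adjuncts to substance use treatment. The app's incremental benefit is part of the stated purpose (Protocol section 1a) and a reason for having two CBT-I arms (SAP 2a.3.a). A reader who accepts the power statement could take a non-significant app comparison as evidence that the app adds nothing.

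**Working it through.** **Inputs from the documents:** 168 randomised, 56 per arm; d = .42; ANCOVA with 3 covariates and, for Aim 2, 3 groups; alpha .05; power .80 where any is named.

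**Assumptions:** two-sided test, a single visit, and no variance explained by covariates.

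**1. Attempt to reproduce the plan's figure.** For two groups, the noncentrality is d × √(n₁n₂/(n₁+n₂)), referred to a noncentral t. For the 3-group ANCOVA, λ = f² × 168 on (2, 162) df, where 162 = 168 − 3 − 3, with f = d/2 = .21.

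| Contrast | Noncentrality | Power at d = .42 | d for 80% power |
|---|---|---|---|
| CBT-I-MA v CBT-I, 56 v 56 | .42 × √28 = 2.22 | 59.6% | 0.53 |
| 3-group ANCOVA, f = .21 | λ = .0441 × 168 = 7.41 | 67.3% | 0.48 (f = .2417) |
| Pooled active v PC, 112 v 56 | .42 × √37.33 = 2.57 | 72.3% | 0.46 |
| 84 v 84 (not the design) | .42 × √42 = 2.72 | 77.2% | 0.43 |

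Removing 3 df for the covariates changes pairwise power by less than .001. If the 3-group F is instead computed with both active arms .42 above PC, f = .42 × √2/3 = .198 and power is 61.8%. None of these two-sided readings reaches 80%.

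**2. Inputs that would bring the claim to 80%.** If d is in unadjusted SD units, the covariates would need R² of about .38 pairwise, .25 for the 3-group F, or .17 pooled. One-sided alpha .05 gives 71% pairwise and 82% pooled.

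**3. What the planned model might add.** Take the mean of three follow-ups adjusted for baseline, with full data and d in single-visit SD units. The variance factor is v = (1 + 2ρ_f)/3 − ρ_b², and the effective d is .42/√v. Pairwise power on 109 df is below. The correlations are my assumptions.

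| ρ_b (baseline) | ρ_f (between visits) | v | Power |
|---|---|---|---|
| .3 | .8 | .777 | 71% |
| .3 | .7 | .710 | 74% |
| .5 | .8 | .617 | 80% |
| .4 | .6 | .573 | 83% |
| .5 | .5 | .417 | 93% |

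Reaching 80% requires v of about .618 or less. A less favourable pair (.2, .9) gives v = .893 and 64%.

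**4. The larger hypothesised effects, full data.** At d = .56, power is 84% pairwise and 93% pooled; d = 1.4 is far above any detectable value in step 1. For 20% v 50% abstinence with 56 per arm, z = [.30 × √56 − 1.96 × √(2 × .35 × .65)] / √(.16 + .25) = 1.44, so power is 93%.

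**5. Loss after randomisation.** The 187 recruited covers only loss before randomisation (187 × .9 = 168). SAP 2a.3.f expects 80% to complete all follow-ups. If the other 20% contributed nothing (about 45 per arm), pairwise power at d = .42 would be 50%, and the d for 80% power would be 0.60 pairwise and 0.52 pooled. This is a worst case, since the mixed model is chosen for "its ability to include all available data, not just data from patients who complete assessments".

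**6. Precision of the app contrast.** The 95% CI half-width at a single visit is 1.98 × √(2/56) = 0.37 SD.

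**The case against.** The strongest reply is that the shortfall depends on inputs I supplied. The SAP names three covariates, and setting R² to zero makes them do nothing. The hypotheses are directional. With modest R² or a one-sided test the pooled primary contrast passes 80%. This stands as far as it goes: for the primary-aim statements, the fair reading is that d = .42 cannot be reproduced from what is stated. But a sample size claim needs its inputs stated, and the SAP gives neither an R² nor a one-sided test. The app comparison is short either way: one-sided testing leaves it at 71%, and it needs R² of about .38.

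Second, the trial will be analysed by a baseline-adjusted repeated-measures model, so 60% is not necessarily its real power. That is correct, and the finding is against the stated justification, not proof that the model is underpowered. The range in step 3 is illustrative only, and nothing in the documents favours either end.

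Third, the SAP already labels the app comparison exploratory, and the primary hypotheses concern larger effects. Both are true and limit the weight of the point. They do not make the power statement correct, and the SAP makes it under both aims.

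Two smaller points also stand. The .80 target is carried over from the mediation and abstinence sentences. And d = 1.4 comes from sleep disturbance during withdrawal, not cannabis use, so step 4 shows only that such an effect would be detected, not that it is likely.

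**Conclusion.** The concern holds. On the stated ANCOVA basis, 168 Veterans give about 60% power at d = .42 for CBT-I-MA against CBT-I, 67% for the 3-group test and 72% for pooled active arms against PC, all below .80. This assumes two-sided alpha .05, one visit, full data and no covariate gain. On that basis a true app effect of .42 would be missed about 4 times in 10. With the planned model the miss rate could be lower, but by an amount that depends on correlations the SAP does not state.

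The error is confined to the d = .42 statements and to the closing claim about all expected effects, which includes the app effect. With full data, detection of d = .56, d = 1.4 and 20% v 50% abstinence is not in question. It should be fixed, but it does not threaten the main hypotheses.

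**What to change.** Keep n = 168 and replace the d = .42 statements with one of the following.

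- **(a) State the detectable effects.** At two-sided alpha .05, a single visit and no covariate gain, 168 (56 per arm) gives 80% power for d of about 0.53 pairwise, 0.48 for the 3-group ANCOVA and 0.46 for pooled active arms against PC. If 20% contributed no follow-up data, the worst-case values are 0.60 pairwise and 0.52 pooled.
- **(b) Rely on the planned model.** State and justify the assumed baseline and between-visit correlations, with the resulting power. The values in step 3 show the sensitivity (71% to 93% over the five pairs tabulated, 64% for the less favourable pair) and do not replace justified inputs.

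In either case:

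- Limit the closing adequacy claim to the larger hypothesised effects (d = .56, d = 1.4, 20% v 50% abstinence).
- Alongside the power statement, repeat that the app comparison is exploratory, and add that it will be reported as an estimate with a 95% CI, so that a null result is not read as no added benefit.
- For mediation, note only that 168 carries no allowance for loss after randomisation.

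The cost is SAP wording: no extra participants, visits or change of analysis. The stated sensitivity for the app comparison becomes less favourable, or the assumed correlations have to be justified.
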